7.0 Randomisation

This is a randomised controlled trial therefore neither the participants nor their physicians will be able to choose the participant's colonoscopy method. The method will be allocated randomly using a computer-based algorithm. This is to ensure that the groups of participants receiving each of the different methods are similar.

The SSP must confirm the eligibility of a patient in the patient's medical notes prior to randomisation.

Participant randomisation will be performed by the SSP using a central randomisation system.

Within 2 days prior to a colonoscopy list (after sending out the bowel preparation kit to those patients), the SSP should randomise the patients on that list to either an enhanced or non-enhanced colonoscopy. This can be done either by telephone or by the internet:

Telephone (Mon – Fri, 9am-5pm): [name]

Internet (Anytime): http://www.wctu.org.uk/rando

Please consult the additional "CONSCOP Trial Randomisation Service User Guide" document for detailed instructions as to how to do this.

Once randomisation is complete, the SSP should enter the trial number that they are given by the central system onto a label on the patient's notes.

ClinicalTrials.gov.: NCT01972451 Page **21** of **42**

8.0 Trial interventions

All participants will undergo a routine colonoscopy test as part of the National Bowel Cancer Screening programme in Wales (BSW).

An approved BSW Screening Colonoscopist who has satisfied the training requirements to carry out colorectal cancer screening on a designated bowel cancer screening endoscopy list will carry out the colonoscopic procedure. During the endoscopy test, titrated sedation in the form of a benzodiazepine (midazolam) and or an opioid analgesic (Pethidine, fentanyl) is offered to the participant unless specifically declined by the patient as per routine practice. The nurse present in the endoscopy room then monitors the participants' physiological parameters and comfort scores closely during the course of the procedure. During the procedure, antispasmodic agents may be given if there is no contraindication. In addition to endoscopy nurses, every BSW list has an SSP who is present in the room and will collect data about the procedure. If there are any polyps detected then they will be removed in the standard manner. The process described above is standard practice in the Bowel Cancer Screening Programme.

8.1 Trial Arm A: Colonoscopy without enhanced dye:

Participants will undergo colonoscopy as per standard procedure described above.

8.2 Trial Arm B: Colonoscopy with enhanced dye

For eligible participants who are randomised to the dye enhanced colonoscopy group, standard procedure described above will be followed. In addition to this, once the caecum is reached a contrast dye (indigo carmine) will be sprayed on the surface of the right colon either using a spray pump or spray catheter through the colonoscope. This will require specific training (to be provided by the Research Team to the local colonoscopists and SSPs) to ensure standardisation of technique of spraying the dye as well as recognise appearances of adenomas and serrated polyps under indigo carmine dye. The standard colonoscopy procedure takes on average 30 minutes with the enhanced procedure estimated to take only an extra 12 minutes and no longer than 15 minutes. Overall procedure times may vary depending on therapy being required for polyp removal.

Indigo carmine is a blue contrast dye that pools in the crevices and valleys between the mucosal projections and highlights topography and it does not stain cells. It is a safe food colouring agent (Food standards agency-EU approved additive E number: E132) (27) and is already been used routinely in various endoscopy procedures in standard clinical practice. The technique of contrast enhanced colonoscopy (or chromoendoscopy) with the use of dye spray has been investigated in numerous studies in different settings and in almost all studies has been demonstrated to increase polyp detection. A Cochrane review on the topic of contrast enhanced colonoscopy has also analysed studies using the dye spray technique though not in the setting of screening and found a positive correlation between polyps detected and use of the technique (2). Pan colonic dye spray during colonoscopy already forms part of standard practice in other settings such as colonoscopic surveillance for neoplasia detection in high-risk cases of inflammatory bowel disease and is part of national guidelines in that setting. (25, 28)

8.2.1 Drug interactions

There are no known interactions of any medicinal products with Indigo carmine. Anyone with a known allergy to a food colouring agent will be excluded.

ClinicalTrials.gov.: NCT01972451 Page **22** of **42**

8.2.2 Supply of dye

Indigo carmine dye spray *used for study patients will delivered to sites every 2 months. The amount will be based upon recruitment.* (see section 5).

ClinicalTrials.gov.: NCT01972451 Page 23 of 42

9.0 Trial assessments

9.1 Data captured after colonoscopy list

For those patients who consented to participate in the trial, the following data should be recorded on the CONSCOP Colonoscopy Case Report Form (CRF) for each patient by the SSP:

- 1. Demographics: smoker/non-smoker (never smoked)/ex smoker
- 2. Was enhanced dye given
- 3. The presence of other factors that can cause a difficult colonoscopy: i.e.
 - (a) previous abdominal surgery
 - (b) presence of diverticular disease
- 4. Resource utilisation data (Llandough only):
 - (a) amount of dye and dilutant used (b) was a scope guide used
 - (c) any other resource use (additional accessory use including clips, sample pots etc)
- 5. Endoscopist assessment of procedural difficulty
- 6. Use of patient position change, adequate insufflation, repetitive examination of colonic segments, examination of flexures and proximal sides of folds, use of torque to flatten folds, and suctioning of liquid

The following information must be entered into BSIMS by the SSP (the SSP will be asked on the CONSCOP Colonoscopy CRF to confirm that they have entered this data) after the procedure:

- 1. Demographics: age, sex
- 2. Total Procedure time (a. start time and b. end of procedure)
- 3. Withdrawal time (a. time of reaching anus minus b. time of reaching caecum)
- 4. Caecal intubation
- 5. Whether the colonoscopy was complete or incomplete (extent of examination i.e. caecum, ileum etc.)
- 6. If colonoscopy incomplete then reason for this (e.g. difficult procedure, inadequate bowel preparation)
- 7. Adverse events (immediate complications) see section 10 for further information for reporting these as SAEs to WCTU
- 8. Data on bowel preparation and quality
- 9. Participant comfort scores (during and after procedure)
- 10. Resource utilisation data:
 - (a) How much sedation and antispasmodics used

The following histology data will be entered into BSIMS:

- 11. The histology report must be scanned and uploaded to BSIMS as soon as it becomes available
- 12. Total number of polyps (polyp detection rate)
- 13. Endoscopic and histological polyp characteristics (description of location, size and morphology)
- 14. Polyp retrieval rate
- 15. Total number of right sided polyps
- 16. Total number of adenomas

ClinicalTrials.gov.: NCT01972451 Page **24** of **42**

Public Health Wales will provide this BSIMS data to WCTU for analysis.

9.2 Central review of polyps found at the splenic flexure or above

After local reporting, all polyps found at the splenic flexure or above in all trial participants should be sent for central review (see section 13). Using data uploaded to BSIMS (see 9.1 above), the central study team will work out which patients had right sided polyps and will request these directly from the appropriate local pathology department. The local pathology department will send the requested paraffin blocks to the pathology laboratory in Cardiff following the instructions in the letter.

9.3 Follow up in routine datasets of all patients up to 30 days after colonoscopy

Public Health Wales will obtain the following data from routine datasets for each participant:

7 day and 30 day hospital re-admission rates (late complications)

Public Health Wales will provide this BSIMS data to WCTU for analysis.

9.4 Longer term follow up

Patients will be asked to optionally consent to longer term follow up by Public Health Wales to allow the following data to be obtained after the completion of this study protocol:

- Cancer incidence
- Mortality and causes of death

Public Health Wales will provide this BSIMS data to WCTU for analysis.

9.5 Completion of CRFs

The top copy of each completed CRF should be returned to the WCTU for data entry **at the end of each week**. The remaining copy is to be retained at the local site. In accordance with the principles of GCP, the PI is responsible for ensuring accuracy, completeness, legibility and timeliness of the data reported to the WCTU in the CRFs.

CRF pages and data received by the WCTU from participating trial sites will be checked for missing, illegible or unusual values (range checks) and consistency over time.

If missing or questionable data are identified, a data query will be raised on a data clarification form. The data clarification form will be sent to the relevant participating site. The site shall be requested to answer the data query or correct data on the data clarification form. The case report form pages should not be altered.

All answered data queries and corrections should be signed off and dated by a delegated member of staff at the relevant participating site. The completed data clarification form should be returned to the WCTU and a copy retained at the site along with the participants' CRFs.

The WCTU will send reminders for any overdue data. It is the site's responsibility to submit complete and accurate data in timely manner.

ClinicalTrials.gov.: NCT01972451 Page **25** of **42**

10.0 Safety reporting and pharmacovigilance

The following definitions are in accordance with GCP. Screening unit staff will be trained by the Research Team in adverse event reporting at the same time as they are trained in trial methods (see section 5.0).

Adverse Event (AE): Any untoward medical occurrence in a clinical trial participant which does not necessarily have a causal relationship with their involvement in the study. An AE can therefore be any unfavourable or unintended sign (including abnormal laboratory finding), symptom, or disease. Examples are:

- A patient is injured as a result of a medical device failure or misuse
- A patient's treatment is interrupted or compromised by medical device failure
- A patient's health deteriorates due to medical device failure or an allergic reaction to the dye

Serious Adverse Event (SAE): Any adverse event that:

- Results in death
- Is life-threatening*
- Requires hospitalisation or prolongation of existing hospitalisation**
- Results in persistent or significant disability or incapacity
- Consists of a congenital anomaly or birth defect
- Is otherwise considered medically significant by the investigator ***
- * Note: The term "life-threatening" in the definition of serious refers to an event in which the participant was at risk of death at the time of the event; it does not refer to an event which hypothetically might have caused death if it were more severe.
- ** Note: Hospitalisation is defined as an in-patient admission, regardless of the length of stay, even if the hospitalisation is a precautionary measure, for continued observation. Pre-planned hospitalisation e.g. for pre-existing conditions which have not worsened or elective procedures does not constitute an adverse event.
- *** Note: Other events that may not result in death or are not life-threatening may be considered as a serious AE when, based upon appropriate medical judgement, the event may jeopardise the participant and may require medical or surgical intervention to prevent one of the outcomes listed above.

Serious Adverse Event relating to colonoscopy and/or colonoscopy with enhanced dye: Any serious event occurring in a clinical trial participant for which there is reasonable possibility that it is related to either the colonoscopy procedure or the use of enhanced dye.

Suspected Unexpected Serious Adverse Event (SUSAE): These are any adverse events that are serious as defined above, thought to be related to either the colonoscopy procedure or the use of enhanced

ClinicalTrials.gov.: NCT01972451 Page **26** of **42**

dye but is 'unexpected' i.e. an adverse reaction, the nature and severity of which is not consistent with the currently known information about the medical procedure.

10.1 Causality Assessments

The Principal Investigator (or another delegated medically qualified doctor from the trial team) and Chief Investigator (or another medically qualified doctor from the Trial Management Group) will assess each SAE to determine the causal relationship with the procedure, and will answer 'yes' or 'no' to the question "Do you consider that there is a reasonable possibility that the SAE may have been caused by the procedure or the use of enhanced dye?".

The causality assessment given by the Principal Investigator (or delegate) cannot be downgraded by the Chief Investigator (or delegate), and in the case of disagreement both opinions will be provided.

10.2 Expectedness Assessments

The Chief Investigator (or another delegated appropriately qualified individual) will assess each SAE to perform the assessment of expectedness.

SAEs which add significant information on specificity or severity of a known, already documented adverse event constitute unexpected events. For example, an event more specific or more severe than that described below is considered unexpected. The list below provides the expected adverse reactions associated with the colonoscopy procedure:

- Abdominal Pain
- Heavy bleeding (including from polyp removal) requiring unexpected admission, surgery or transfusion
- Perforation of bowel requiring unexpected admission, surgery or transfusion
- Allergy to dye
- Hyperventilation
- Vasovagal episode
- Anxiety

When to report:

Adverse events (AE) should be graded using the NCI Common Terminology Criteria for Adverse Events (CTCAE) Version 4.03.

For all adverse events, colonoscopy with or without enhanced dye complications occurring up to 60 days after the procedure:

- Grade 3-4 report on SAE form, only during procedure or if patient is admitted to hospital
- Deaths due to any cause

10.3 Participating screening unit SAE reporting responsibilities

All SAEs that a participating unit becomes aware of should be reported to WCTU using the trial specific SAE forms provided within 24 hours of knowledge of the event.

ClinicalTrials.gov.: NCT01972451 Page **27** of **42**

The PI should assess the SAE to see if it is related or not related to the trial intervention. In the PIs absence a medically qualified delegate on the delegation log should complete the assessments. A separate form must be used to report each event. SAE forms and SAE fax cover sheet should be faxed to the WCTU within 24 hours of knowledge of the SAE.

WCTU SAE [contact]

Please contact the WCTU immediately if you have a query about the classification of an AE or SAE.

An SAE form is not considered complete unless the following details are provided:

- Full participant trial number
- An adverse event/reaction
- A completed assessment of the seriousness and causality as performed by the PI or an appropriately qualified delegated doctor registered on the delegation log. N.B. It is a requirement of GCP that a clinician provides this clinical assessment. SSPs, Nurses and other local trial staff should NOT complete this section of the SAE CRF, or authorise SAE CRFs. If they do so, the SAE form will be immediately queried by WCTU trial staff and a clinician review must be gained as soon as possible and the SAE form resubmitted with this information.

If any of these details are missing, you will be contacted by the WCTU and the information must be provided as soon as it becomes available.

Sites are required to follow up SAEs until resolution and respond to queries from WCTU regarding follow up information as soon as possible.

Serious adverse events should continue to be reported until 30 days after the participant has their colonoscopy.

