15.6 Data protection

The WCTU will act to preserve patient confidentiality and will not disclose or reproduce any information by which participants could be identified, except where specific consent is obtained. All data leaving sites and Public Health Wales and going to WCTU will have had all identifiers (name, date of birth, postcode, NHS number etc). The BSW number (a reference number only meaningful to staff in the BCSP) will be provided to WCTU to allow linkage with data from CRFs.

Data will be stored in a secure manner and will be registered in accordance with the Data Protection Act 1998. The data custodian for this trial is the Director of the WCTU. The sample custodian for the trial is [name].

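### No in-study source systematically finds deaths, and the 30-day re-admission extract has no stated route into SAE reporting

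*Protocol*

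**What the plan says.** **What must be reported.** Section 10.0 defines an SAE by the usual criteria. One of them is "Requires hospitalisation or prolongation of existing hospitalisation", with no grade threshold. Section 10.2 says when to report. It covers "colonoscopy with or without enhanced dye complications occurring up to 60 days after the procedure" and lists two items: "Grade 3-4 report on SAE form, only during procedure or if patient is admitted to hospital" and "Deaths due to any cause".

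**Who reports, and until when.** Section 10.3 states: "All SAEs that a participating unit becomes aware of should be reported to WCTU". It allows 24 hours from knowledge of the event and ends SAE reporting 30 days after the colonoscopy.

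**What is collected.**
- Section 9.1 has the SSP enter adverse events into BSIMS after the procedure, described as immediate complications. This is the only data item that points to section 10.
- Section 9.3 has Public Health Wales obtain re-admissions at 7 and 30 days for each participant from routine datasets, and labels them late complications. It adds: "Public Health Wales will provide this BSIMS data to WCTU for analysis".
- Section 9.4 covers mortality and cause of death. It begins: "Patients will be asked to optionally consent to longer term follow up". These data are to be obtained once the study protocol has been completed.

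**What allows linkage.** Section 15.6 says that the BSW number "will be provided to WCTU to allow linkage with data from CRFs".

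**The concern.** The reporting duty in section 10.2 is wider than the means of finding the events. The protocol describes no visit, call or questionnaire after discharge. It nevertheless expects late complications, since section 9.3 uses that label, and the expected reactions in section 10.2 include bleeding and perforation leading to unplanned admission.

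Adverse events are a listed endpoint in the synopsis. Sections 10.1, 10.2 and 10.4 build causality and expectedness assessments, SUSAE reports and a 12-monthly list to the ethics committee on the SAE forms received. An event that never reaches a form passes through none of these steps. WCTU could hold a re-admission in its analysis data with no matching SAE form, and nothing in the protocol would prompt a query.

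**Working it through.** No arithmetic bears on the main point, and the protocol has no figure to reproduce. The check is to set each kind of event against the source that would find it and the route from that source to an SAE form.

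| Event | Duty to report | Source within the study | Stated route to an SAE form |
|---|---|---|---|
| Immediate complication | 10.0, 10.2, 10.3 | SSP entry in BSIMS (9.1) | Yes: 9.1 refers to section 10 |
| Re-admission to day 30 | 10.2 if Grade 3-4; 10.0 with 10.3 if any SAE | Routine-data extract for each participant (9.3) | None from the extract; only unit awareness (10.3) |
| Admission on days 31-60 | 10.2 if Grade 3-4; outside the 10.3 window | None | Only unit awareness |
| Death, days 0-30 | 10.2, 10.3 | None | Only unit awareness |
| Death, days 31-60 | 10.2; outside the 10.3 window | None | Only unit awareness |

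**Deaths.** Section 9.3 lists re-admissions and nothing else, so a death outside hospital leaves no trace in it. Section 9.4 does list mortality, but only for those who agree to it and only after the protocol is complete. It cannot support reporting during the trial.

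**Re-admissions to day 30.** The data exist for each participant and reach WCTU, which also holds the BSW number. The missing piece is the hand-off. Section 10.4 starts WCTU's evaluation when an SAE is received, and section 15.4 delegates to Public Health Wales only the provision of data under section 9. Neither section compares the extract with the SAE forms.

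**The window.** Section 10.2 runs to day 60; section 10.3 and the section 9.3 extract stop at day 30. If section 10.2 is followed, 60 − 30 = 30 days, half of the reporting period, have no data source. If section 10.3 is followed, the 60-day statement in section 10.2 is wrong. The two cannot both stand.

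**The case against.** The best defence has four parts.

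- **Tying the duty to awareness is normal.** It fixes when the 24-hour clock starts and is not an error. This stands. The weakness is that no active source sits behind it for deaths, and that the one active source for re-admissions is not connected to it.
- **The trial is low risk.** There is no investigational medicinal product, section 4.1 puts the risk no higher than standard care, and section 11.2 refers to a monitoring plan that is not shown. A check of the extract against SAE forms could sit in that plan. This is fair for the matching step. It does not supply a death field that section 9.3 omits, and it does not resolve 60 days against 30.
- **A reader might infer that nothing after discharge finds any event, or that section 10.2 demands a report of every admission.** The documents support neither. Section 9.3 finds re-admissions to day 30 for each participant and describes the data as coming from BSIMS. Section 10.2 limits admissions to Grade 3-4 events; the wider duty comes from section 10.0 read with section 10.3.
- **A reader might also infer that reporting will differ by arm, because the trial is open, or try to count the missed SAEs.** Nothing in the protocol shows that staff would follow one arm more closely, and the 30-day re-admission data do not depend on unit awareness. The protocol gives no event rate or awareness rate from which to derive a count.

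**Conclusion.** The point holds as a gap in ascertainment plus one direct contradiction.

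- Deaths, which section 10.2 requires to be reported whatever the cause, have no systematic source during the study for any of the 1320 planned participants.
- Re-admissions to day 30 are found for each participant but have no stated route into SAE assessment.
- The 60-day and 30-day statements conflict, and days 31 to 60 have no source other than unit awareness.

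The conclusion rests on the protocol as written. It assumes that no unseen operational document already adds deaths to the extract or matches the extract to SAE forms. It does not say that the reporting duty is bound to fail, since units may learn of many events through routine contact. It says that the plan gives no assurance of completeness. For a low-risk feasibility trial this is an inexpensive improvement to safety reporting and does not threaten the main feasibility objectives.

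**What to change.** 1. Reconcile sections 10.2 and 10.3 so that a single reporting window is stated. This comes first because the other changes follow it.
2. In section 9.3, add death (date and cause) within the reconciled window to the Public Health Wales extract for all participants, not dependent on the optional consent in section 9.4. Align the extract's re-admission period with the same window.
3. In sections 9.3 and 10.4, state that the extract is delivered periodically during the trial. State also that WCTU matches each admission and death by BSW number to the SAE forms held, and queries the site where no form exists. The site then judges whether the event meets the reporting criteria.

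The cost is extra fields in an extract already planned for each participant, periodic delivery, a listing check at WCTU with a few site queries, and a check that the consent wording covers deaths obtained outside section 9.4. No additional patient contact is needed.
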